The primary endpoint is the number of bleeding episodes during at least 24 weeks from treatment onset. *All treated bleeding episodes will be considered for this endpoint, including bleeding episodes recorded as post-surgical or caused by surgery or other medical for dental procedures.*

The primary endpoint will be estimated using negative binomial regression with log of exposure time ~~in~~ *(the included observational period of the main part)* ~~phase~~ as offset, providing an actual estimate of the ABR as well as a corresponding 95% confidence interval. *The offset for first CPoC criterion is the log of the individual exposure time at the last dose level reached at the time of analysis excluding the 2 weeks run-in period for subjects on 0.15 mg/kg. The offset for the second criterion is the log of the individual exposure time in the main part.*

Section 17.5 Additional analyses

An additional evaluation of the primary endpoint will be made, including actual concizumab dose level *(interpreted as the patient's last dose level)* as additional factor in the primary analysis model specified above. Point estimates and 95% confidence interval will be provided for the ABR at the different dose levels of concizumab (0.15, 0.20 and 0.25 mg/kg). Furthermore, *a series of analyses* ~~an analysis~~ with individual steady state PK/PD assessments included as covariates in the negative binomial regression model as specified for the primary analysis will be performed in order to evaluate possible associations between PK/PD and ABR that potentially could guide dose-selection. The referred steady-state PK/PD assessments comprise the concizumab trough level, maximum plasma concentration (C_{max}) of concizumab, TFPI value prior to the last s.c. dose administration, peak thrombin generation (nM), Endogenous thrombin potential (nM*min) and velocity index (nM/min).

Section 17.6.1 Supportive secondary efficacy endpoints

- The number of bleeding episodes during *at least* 76 weeks from treatment onset
- The number of spontaneous bleeding episodes during at least 24 weeks from treatment onset
- The number of spontaneous bleeding episodes during *at least* 76 weeks from treatment onset

The supportive secondary endpoints will be estimated using the same negative binomial regression model as the primary endpoint *and performing the same two analyses as for the primary endpoint; one only including observations from the period on the last dose level and one including the entire escalation pattern.*

Section 17.6.2 Supportive secondary safety endpoints

- Number of treatment-emergent adverse events (TEAEs) during at least 24 weeks from treatment onset
- Number of TEAEs during *at least* 76 weeks from treatment onset
- Occurrence of anti-concizumab antibodies during at least 24 weeks from treatment onset
- Occurrence of anti-concizumab antibodies during *at least* 76 weeks from treatment onset

Protocol Amendment no 3
 Trial ID: NN7415-4255
 UTN: U1111-1179-3872
 EudraCT No.: 2016-000614-29

~~CONFIDENTIAL~~

Date: 28 August 2018
 Version: 1.0
 Status: Final
 Page: 23 of 29

Novo Nordisk

- Change from baseline of fibrinogen during 24 weeks from treatment onset
- Change from baseline of fibrinogen during *at least 76 weeks* from treatment onset
- Change from baseline of D-dimer during 24 weeks from treatment onset
- Change from baseline of D-dimer during *at least 76 weeks* from treatment onset
- Change from baseline of prothrombin fragment 1 + 2 (F1 + 2) during 24 weeks from treatment onset
- Change from baseline of F1 + 2 during *at least 76 weeks* from treatment onset
- Change from baseline of prothrombin time (PT) during 24 weeks from treatment onset
- Change from baseline of PT during *at least 76 weeks* from treatment onset
- Change from baseline of activated partial thromboplastin time (APTT) during 24 weeks from treatment onset
- Change from baseline of APTT during *at least 76 weeks* from treatment onset
- Change from baseline of anti-thrombin (AT) during 24 weeks from treatment onset
- Change from baseline of AT *after at least 76 weeks* from treatment onset

Adverse Events will be coded using the most recent version of Medical Dictionary for Regulatory Activities (MedDRA) coding.

A Treatment Emergent Adverse Event (TEAE) is defined as an event that has onset from the first exposure to treatment until the last visit in the trial. *Adverse events collected among permanently prematurely discontinued from trial product due to a safety concern patients after visit 17 in the possible extended follow-up (ref section 8.1.4) are not considered treatment emergent.* Treatment-emergent adverse event endpoints will be summarised by system organ class, preferred term, seriousness, severity and relation to trial product. All Adverse events will further be listed.

Section 17.6.3 Supportive secondary pharmacokinetic endpoints

- Concentration of concizumab prior to the last dose administration at 24 weeks
- Concentration of concizumab prior to the last dose administration *after at least 76 weeks*

Section 17.6.4 Supportive secondary pharmacodynamic endpoints

Plasma free TFPI concentration

- Value prior to the last dose administration at 24 weeks
- Value prior to the last dose administration *after at least 76 weeks*

Thrombin generation

- Peak thrombin generation (nM) prior to the last dose administration at 24 weeks
- Peak thrombin generation (nM) prior to the last dose administration *after at least 76 weeks*
- Endogenous thrombin potential (nM*min) prior to the last dose administration at 24 weeks
- Endogenous thrombin potential (nM*min) prior to the last dose administration *after at least 76 weeks*

Protocol Amendment no 3
 Trial ID: NN7415-4255
 UTN: U1111-1179-3872
 EudraCT No.: 2016-000614-29

~~CONFIDENTIAL~~

Date: 28 August 2018
 Version: 1.0
 Status: Final
 Page: 24 of 29

Novo Nordisk

- Velocity index (nM/min) prior to the last dose administration at 24 weeks
- Velocity index (nM/min) prior to the last dose administration *after at least 76 weeks*

Section 17.7.2 Exploratory patient-reported outcome endpoints

- Change in Hemo-TEM after 24 weeks from treatment onset
- Change in Hemo-TEM after *at least 76 weeks* from treatment onset
- Change in SF-36v2 after 24 weeks from treatment onset
- Change in SF-36v2 after *at least 76 weeks* from treatment onset
- Change in SDS after 24 weeks from treatment onset
- Change in SDS after *at least 76 weeks* from treatment onset
- Change in TSQM after 24 weeks from treatment onset
- Change in TSQM after *at least 76 weeks* from treatment onset
- Change in SIAQ-ISRQ after 24 weeks from treatment onset
- Change in SIAQ-ISRQ after *at least 76 weeks* from treatment onset
- Status of PGI-C after 24 weeks from treatment onset
- ~~Change in~~ H-DAT after *at least 76 weeks* from treatment onset

Patient reported outcomes (PROs) will be collected using questionnaires at visits 1, 2, 4, 5, 6, 7, 8, 9, 10 and *at either visit 15.1 or 16*.

Section 17.7.2 Exploratory patient-reported outcome endpoints

VERITAS-Pro[®] or VERITAS-PRN[®], SF-36v2, SDS, TSQM, ~~H-DAT and SIAQ-ISRQ~~ will be scored according to their respective scoring algorithms. Change from visit 2 to visit 9 and change from visit 2 to visit *15.1 or 16 for SF-36v2, SDS, TSQM and SIAQ-ISRQ* will be described.

Section 17.7.3 Exploratory pharmacokinetic and pharmacodynamic endpoints

- Concentration of concizumab over time during 24 hours PK assessment
- Concentration of free TFPI over time during 24 hours PD assessment
- Thrombin generation over time during 24 hours PD assessment
 - Peak of thrombin generation time during 24 hours PD assessment
 - ETP time during 24 hours PD assessment
 - Velocity index time during 24 hours PD assessment

All endpoints referring to a time frame of either 24 weeks or of at least 24 weeks will be evaluated in the main part of the trial.

All endpoints referring to a time frame of *76 or more weeks* will be evaluated in the extension part of the trial.

Section 17.8 Interim analysis (Figure 17-1)

[figure not shown]
Protocol Amendment no 3
 Trial ID: NN7415-4255
 UTM: U1111-1179-3872
 EudraCT No.: 2016-000614-29

CONFIDENTIAL

Date:
 Version:
 Status:
 Page:

28 August 2018
 1.0
 Final
 25 of 29

Novo Nordisk

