8.1.9 Treatment period - Main part

8.1.9.1 Visit 2 (Assessment, 1st concizumab treatment at site)

Visit 2 should be scheduled 14 to 21 days after visit 1. The date of visit 2 will be considered as trial day 1.

Before any concizumab administration it is important to verify the in/exclusion criteria again and review central laboratory test results from screening.

The patient must be in a non-bleeding state at the time of first administration with concizumab and should not have received any FVIII treatment for prophylaxis or for treatment of a bleeding episode within a period of 48 hours prior to dosing.

Patients will be asked to complete the ePRO questionnaires before any other trial related activities are performed according to section [8.6.1](#);

- Hemo-TEM,
- SF-36v2,
- SDS,
- TSQM,

Protocol
 Trial ID:NN7415-4255
 UTN:U1111-1179-3872
 EudraCT no.:2016-000614-29

~~CONFIDENTIAL~~

Date: 28 August 2018
 Version: 5.0
 Status: Final
 Page: 46 of 127

Novo Nordisk

○ SIAQ-ISRQ

All protocol assessments must be performed before 1st administration of concizumab. Vital signs must be assessed both before and after concizumab administration.

Assessment results from concomitant medication, vital signs, Body measurements (weight only) and details of adverse events must be entered into the eCRF.

At this, the 1st treatment visit, the allocated dose of concizumab will be given. Concizumab will be administered at the trial site supervised by medically trained trial staff.

The time point at which the completion of the first dose takes place corresponds to Time on treatment = 0 and must be recorded in the eCRF.

The patient must be observed at the trial site for at least 2 hours after the administration of the first dose of concizumab.

In order to determine the correct amount of the patient's daily dose of concizumab, until next scheduled visit, investigator will consult the dosing-table in the TMM on basis of the patient's current body weight.

Investigator will communicate any the daily dose of concizumab to the patient and record the dose for the coming home treatment period in the eCRF.

Prior to the first dose a dispensing call must be performed in the IWRS.

At the visit the patient will be provided with trial product (concizumab and if necessary rFVIII (turoctocog alfa)) and injection kits as well as an eDiary device to be able to conduct and report home treatment until the next scheduled visit.

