8.2.2 Concomitant illness and medical history other than haemophilia

A **concomitant illness** is any illness, other than haemophilia A, that is present at the start of the trial (i.e. at the first visit) or found as a result of a screening procedure or other trial procedures performed before first exposure to trial product. All concomitant illnesses should be reported in the Concomitant illness forms in the eCRF except information on haemophilia A which is to be reported in the Haemophilia Medical history section of the eCRF.

Medical history is a medical event, other than haemophilia A, which the patient has experienced in the past. Only relevant medical history should be reported. The information collected for concomitant illness and medical history should include diagnosis, date of onset and date of resolution or continuation, as applicable. Any change to a concomitant illness should be recorded during the trial. A clinically significant worsening of a concomitant illness must be reported as an AE.

It must be possible to verify the patient's medical history in source documents such as patient's medical record:

If a patient is not from the investigators own practice; the investigator must make a reasonable effort to obtain a copy of the patient's medical record from relevant party e.g. primary physician. See section [6.2](#) and [6.3](#) for full description of the selection criteria. The investigator must document any attempt to obtain external medical information by noting the date(s) when information was requested and who has been contacted.

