8.5.2.5 Coagulation parameters

- Fibrinogen
- Prothrombin time (PT) including INR
- D-dimer
- Prothrombin fragment 1+2
- Activated partial thromboplastin time (APTT)
- Antithrombin (AT)

The investigator must evaluate the results and record the outcome as:

- Normal or abnormal
- If abnormal the investigator must:
 - Specify the abnormality
 - Record if the result is clinically significant (Yes/No)
 - If observed before or at screening: record as concomitant illness (section [8.2.2](#))
 - If observed after screening: report an AE/SAE (section [12](#))

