12.1 Definitions

12.1.1 Adverse event

An adverse event (AE) is any untoward medical occurrence in a patient administered a medicinal product, and which does not necessarily have a causal relationship with this treatment.

An AE can therefore be any unfavourable and unintended sign (including an abnormal laboratory finding), symptom or disease temporally associated with the use of a product, whether or not considered related to the product.

An AE includes:

- A clinically significant worsening of a concomitant illness.
- A clinical laboratory adverse event (CLAE): a clinical laboratory abnormality which is clinically significant, i.e. an abnormality that suggests a disease and/or organ toxicity and is of a severity that requires active management. Active management includes active treatment or further investigations, for example change of medicine dose or more frequent follow-up due to the abnormality.

The following should **not** be reported as AEs:

- Pre-existing conditions, including those found as a result of screening or other trial procedures performed before exposure to trial product (pre-existing conditions should be reported as medical history or concomitant illness).
- Pre-planned procedures unless the condition for which the procedure was planned has worsened from the first trial related activity after the patient has signed the informed consent.
- Bleeding episodes and other symptoms (e.g. pain, swelling, synovitis, arthralgia) in connection with bleeding episodes should not be reported as AEs/SAEs unless the event is fatal, life-threatening or evaluated by the investigator as related to trial product or trial procedure. All bleeding episodes and other findings related to underlying disease will be captured in the eCRF/eDiary

The following three definitions are used when assessing an AE:

- **Severity**
 - **Mild** – no or transient symptoms, no interference with the patient’s daily activities.
 - **Moderate** – marked symptoms, moderate interference with the patient’s daily activities.
 - **Severe** – considerable interference with the patient’s daily activities; unacceptable.
- **Causality**
 Relationship between an AE and the relevant trial product(s):
 - **Probable** - Good reason and sufficient documentation to assume a causal relationship.

Protocol
 Trial ID:NN7415-4255
 UTN:U1111-1179-3872
 EudraCT no.:2016-000614-29

~~CONFIDENTIAL~~

Date: 28 August 2018
 Version: 5.0
 Status: Final
 Page: 81 of 127

Novo Nordisk

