12.2 Reporting of adverse events

All events meeting the definition of an AE must be collected and reported. This includes events from the first trial-related activity after the patient has signed the informed consent until visit 16 (end of treatment) for patients enrolling into a subsequent trial with concizumab and at the end of the post-treatment follow-up period (visit 17) for patients not enrolling in to a new trial. The events must be recorded in the applicable eCRF forms in a timely manner; see timelines below in [Figure 12-1](#)

During each contact with the trial site staff, the patient must be asked about AEs and technical complaints, for example by asking: “Have you experienced any problems since the last contact?”

All AEs, either observed by the investigator or patient, must be reported by the investigator and evaluated. All AEs must be recorded by the investigator on an AE form. The investigator should report the diagnosis, if available. If no diagnosis is available, the investigator should record each sign and symptom as individual AEs using separate AE forms.

For SAEs, a safety information form must be completed in addition to the AE form. If several symptoms or diagnoses occur as part of the same clinical picture, one safety information form can be used to describe all the SAEs.

Protocol
Trial ID:NN7415-4255
UTN:U1111-1179-3872
EudraCT no.:2016-000614-29

~~CONFIDENTIAL~~

Date:	28 August 2018	Novo Nordisk
Version:	5.0	
Status:	Final	
Page:	89 of 127	

AESIs regardless of the seriousness, must be reported using the AE form and safety information form

For all non-serious AEs, the applicable forms should be signed when the event is resolved or at the end of the trial at the latest.

Timelines for initial reporting of AEs:

The investigator must complete the following forms in the case report form (CRF)/eCRF within the specified timelines:

- **SAEs:** The AE form **within 24 hours** and the safety information form **within 5 calendar days** of the investigator's first knowledge of the SAE.

Both forms must be signed within 7 calendar days from the date the information was entered in the eCRF.

For SAEs requiring reporting on a specific event form: In addition to the above the specific event form within **14 calendar days** from the investigator's first knowledge of the AE.

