The investigator must ensure that the recording of the worst case severity and seriousness of an event is kept throughout the trial. A worsening of an unresolved AE must be reported as follow up with re-assessment of severity and/or seriousness of the event.

Queries or follow-up requests from Novo Nordisk must be responded to **within 14 calendar days** from the date of receipt of the request, unless otherwise specified in the follow-up request.

SAEs after end of trial: If the investigator becomes aware of an SAE with a suspected causal relationship to the investigational medicinal product occurring to a patient after the patient has ended the trial, the investigator should report this SAE within the same timelines as for SAEs during the trial.

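### The TEAE definition has no worsening clause, so an AE recorded before first dose, unresolved at dosing, that worsens on concizumab is left out of the TEAE count

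*Protocol*

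**What the plan says.** **TEAE definition.** Section 17.6.2 of version 5.0, repeated unchanged in Protocol Amendment no 3, says a TEAE "is defined as an event that has onset from the first exposure to treatment until the last visit in the trial". The only later qualification removes events after visit 17 in the extended safety follow-up. Nothing is said about earlier events that worsen.

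**AE collection.** Section 12.2: "This includes events from the first trial-related activity after the patient has signed the informed consent". Section 8.1.9.1 places visit 2, the first dose, 14 to 21 days after visit 1.

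**Worsening.** Section 12.3: "The investigator must ensure that the recording of the worst case severity and seriousness of an event is kept throughout the trial". It continues: "A worsening of an unresolved AE must be reported as follow up with re-assessment of severity and/or seriousness of the event".

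**Concomitant illness.** Section 12.1.1 lists among things not to be reported as AEs: "Pre-existing conditions, including those found as a result of screening or other trial procedures performed before exposure to trial product". Section 8.2.2 defines concomitant illness in matching terms and adds: "A clinically significant worsening of a concomitant illness must be reported as an AE".

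**Laboratory findings.** Sections 8.5.2.2, 8.5.2.3 and 8.5.2.5 carry the instruction "If observed after screening: report an AE/SAE", with a pointer to section 12. For visit 2, section 8.1.9.1 says: "All protocol assessments must be performed before 1st administration of concizumab".

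**The concern.** Each rule is ordinary alone. Together they leave a gap. The TEAE definition looks only at onset, and the follow-up rule stops a worsening from generating a new event with a new onset. A mild AE from the screening weeks that becomes severe or serious under treatment is then one record with a pre-dose onset and a post-dose worst grade, and it is not a TEAE.

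The number of TEAEs during at least 24 weeks is named in the protocol summary as a key secondary endpoint and as the key safety assessment. TEAEs are to be summarised by seriousness, severity and relation to trial product. The omission runs one way, since only worsenings on drug are dropped, and a single-arm trial has no comparator in which the same under-count would occur. The protocol fixes the definition itself, so an analysis plan that follows it inherits the gap.

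**Working it through.** The protocol gives no figure to reproduce. The check is to follow each type of pre-dose problem through the rules.

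1. **AE arising after consent, unresolved at first dose, then worse on concizumab.** It is collected (12.2). The worsening is follow-up (12.3), including when a non-serious AE becomes serious. Onset stays before first exposure. Under 17.6.2 it is **not a TEAE**. The protocol does not say in terms that a follow-up record keeps its onset date, but that is the plain reading of updating an existing event.
2. **AE arising after consent, resolved, then recurring on concizumab.** The follow-up rule covers only unresolved AEs. The recurrence can be a new AE with onset on treatment: **a TEAE**.
3. **Condition present at visit 1, or found by a trial procedure before exposure.** This is concomitant illness (8.2.2, 12.1.1). Its clinically significant worsening is reported as an AE, with onset at the worsening: **a TEAE**.
4. **Laboratory abnormality first seen at visit 2.** The sample is taken before dosing (8.1.9.1). The wording in 8.5.2 sends a finding made after screening to an AE report, which would lead to case 1. Sections 8.2.2 and 12.1.1 make it concomitant illness, which leads to case 3. The 8.5.2 lines point to section 12, whose own definition excludes such findings. Section 12.5.1 also describes screening as running from visit 1 to dosing at visit 2, whereas section 8.1 lists only visit 1 under the screening part. This is **a wording conflict**, and the better reading is case 3.

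The gap is therefore case 1.

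**Size of the window.** Inputs: 14 to 21 days (8.1.9.1); 33 patients planned to start trial product (6.1); main part of at least 24 weeks = 168 days; total treatment of at least 76 weeks = 532 days.

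- Person-time at risk before first dose: 33 × 14 / 365.25 = 1.26 and 33 × 21 / 365.25 = 1.90 patient-years.
- Relative to the minimum main part: 14/168 = 8.3% to 21/168 = 12.5%.
- Relative to 76 weeks: 14/532 = 2.6% to 21/532 = 3.9%.

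**Number of events.** The protocol gives no AE rate. As an illustration only, an assumed 3 to 6 AEs per patient-year gives 1.26 × 3 = 3.8 to 1.90 × 6 = 11.4 AEs starting before first dose. That counts every such AE. Those that are also unresolved at dosing and then worsen are a subset whose size cannot be derived.

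**The case against.** The strongest reply is that little is lost. Worst severity and seriousness are kept on the record, an AE that turns serious must be reported within 24 hours, all AEs are listed, and the data monitoring committee reviews all safety data. TEAEs are only summarised, with no test or comparator, so no planned decision turns on one or two events. All of this stands, and it limits the consequence. It does not correct the count.

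Three stronger readings are tempting and not supported:

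- *Anything that starts before first dose can never become a TEAE.* Sections 8.2.2 and 12.1.1 contradict this for concomitant illness, and the follow-up rule does not reach AEs that resolved and recurred.
- *Worsening coagulation or liver tests are lost.* Fibrinogen, D-dimer and F1+2 have their own change-from-baseline endpoints in 17.6.2 whatever their AE status. Low fibrinogen and ALT above three times the upper limit at screening are exclusions (6.3), and the combined transaminase and bilirubin pattern without alternative cause must always be reported as an SAE (12.1.2). The visit 2 laboratory route is also only a wording conflict.
- *A number of affected patients can be stated.* That would need AE and visit 2 abnormality rates that the protocol does not give.

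A practical objection also stands in part. Version 5.0 is dated 28 August 2018 and section 7 lists last patient first visit as 16 December 2017, so new visit 2 instructions would reach few or no patients. The TEAE definition, by contrast, is applied at analysis.

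**Conclusion.** The point holds in a narrow form. As written, sections 17.6.2 and 12.3 together exclude from the TEAE endpoints an AE recorded between consent and first dose, unresolved at dosing, that then increases in severity or seriousness on concizumab. This rests on the plain reading that a follow-up entry leaves the onset date unchanged. The exposure is 14 to 21 days per patient, about 1.3 to 1.9 patient-years in all. The expected number of events is small and not derivable from the protocol, but any such event is a deterioration on drug and its omission lowers the count. The events remain in the listings. The 8.5.2 wording for pre-dose visit 2 findings is a secondary inconsistency to be tidied. It is not evidence of further lost events.

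**What to change.** 1. **Section 17.6.2.** Define a TEAE as an event with onset from first exposure, or with onset before first exposure and an increase in severity or seriousness after it. Keep the existing end of the window and the exclusion after visit 17.
2. **Section 12.3.** For AEs ongoing at first dose, capture the date of worsening. The protocol requires only that the worst grade be kept, so it cannot be assumed that this date is already held in the eCRF. With about 33 patients, the few records concerned can be found and reviewed individually. This also avoids changing the AE recording rule for everyone mid-trial, which would itself make counts inconsistent between periods.
3. **Section 8.5.2.** Reconcile the post-screening AE instruction in 8.5.2.2, 8.5.2.3 and 8.5.2.5 with sections 8.2.2 and 12.1.1, so that the status of a pre-dose visit 2 finding is unambiguous. At this stage this mainly settles how existing records are read.

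The cost is one clause in the definition, a small data review, and a TEAE count that may be slightly higher.
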